As of 27 March 2013, a total of 32 on-study deaths were reported in the clinical studies. One of the 32 events was deemed by the investigator to be related to treatment with Ixazomib (pneumonia RSV in Study C16005). The most common cause of death was disease progression.

Potential Benefits

The clinical benefit of ixazomib continues to be studied in a comprehensive and global development plan that involves studies sponsored by Millennium. Ixazomib appears to show early signs of anti-tumor activity as evidenced by at least 50% reduction in disease burden in

some patients, including patients that have been heavily pretreated as well as those with newly diagnosed MM, and prolongs stabilization of the underlying disease in other patients across all ongoing trials. The preliminary findings are favorable when considering historical and currently available therapies for the patient populations evaluated. Though additional data are needed to characterize the clinical benefit of this drug, the emerging data supports expanded development of Ixazomib for the treatment of patients with advanced malignancy.

IFN- α -2b: Description, PK, PD, and safety data

Pegylated IFN- α -2b is a covalent conjugate of recombinant alfa interferon with monomethoxy polyethylene glycol (PEG). The biological activity of pIFN is derived from its interferon α -2b moiety. Interferons exert their cellular activities by binding to specific membrane receptors on the cell surface and initiate a complex sequence of intracellular events. These include the induction of certain enzymes, suppression of cell proliferation, immunomodulating activities such as enhancement of the phagocytic activity of macrophages and augmentation of the specific cytotoxicity of lymphocytes for target cells, and inhibition of virus replication in virus-infected cells. Interferon alfa upregulates the Th1 T-helper cell subset in *in vitro* studies. Please see Section 1790898588 for more background from the [name] lab.

Pegylated IFN has a single PEG-moiety and a molecular weight of 12 kDa and is a conjugate of interferon with polyethylene glycol (PEG). As a single agent therapy it is well tolerated up to 6.0 mcg/kg per week, which achieves an exposure comparable to 180 MIU nonpegylated interferon per week.^{26,43} The conjugate decreases the clearance, thus prolonging the plasma half time ($t_{1/2}$) to approximately 40 hours (in patients with chronic hepatitis) from otherwise 3-7 hours for not conjugated interferon alfa-2b.^{44,45} The prolonged plasma half-life of Peg-interferon achieves a more constant exposure which leads to an increased area under the concentration curve (AUC). This may more effectively inhibit the angiogenesis as repeated injections of low-dose interferon.²⁷ Thereby, the efficacy of the drug may be increased as it has an antiangiogenic effect apart from the immunological effect.

The pharmacokinetics of pIFN allows for administration subcutaneously once weekly and this regimen has shown acceptable safety.⁴⁴ pIFN has been used in different clinical settings such as hepatitis C,⁴⁶ chronic myelogenous leukaemia (CML)⁴⁷, malignant melanoma,²⁶ and mRCC.^{25,26,29,48} Pegylated IFN raises concentrations of effector proteins such as serum neopterin and 2'5' oligoadenylate synthetase, raises body temperature, and causes reversible decreases in leukocyte and platelet counts. The correlation between the *in vitro* and *in vivo* pharmacologic and pharmacodynamic and clinical effects is unknown.

In Hepatitis C studies with pIFN, following a single subcutaneous (SC) dose of PEG-Intron, the mean absorption half-life ($t_{1/2} k_a$) was 4.6 hours. Maximal serum concentrations (C_{max}) occur between 15-44 hours post-dose, and are sustained for up to 48-72 hours. The C_{max} and AUC measurements of PEG-Intron increase in a dose-related manner. After multiple dosing, there is an increase in bioavailability of PEG-Intron. Week 48 mean trough concentrations (320 pg/mL; range 0, 2960) are approximately 3-fold higher than Week 4 mean trough concentrations (94 pg/mL; range 0, 416). The mean PEG-Intron elimination half-life is approximately 40 hours (range 22 to 60 hours) in patients with HCV infection.

The apparent clearance of PEG-Intron is estimated to be approximately 22.0 mL/hr·kg. Renal elimination accounts for 30% of the clearance. Single dose peginterferon alfa-2b pharmacokinetics following a subcutaneous 1.0 µg/kg dose suggest the clearance of peginterferon alfa-2b is reduced by approximately half in patients with impaired renal function (creatinine clearance <50 mL/minute).

The pharmacokinetics of geriatric patients (> 65 years of age) treated with a single subcutaneous dose of 1.0 µg/kg of PEG-Intron were similar in C_{max} , AUC, clearance, or elimination half-life as compared to younger subjects (28 to 44 years in age).

During the 48 week treatment period with PEG-Intron no differences in the pharmacokinetic profiles were observed between male and female patients with chronic hepatitis C infection.

In cancer patients, Bukowski et al conducted a phase I/II study using pIFN- α -2b to determine the MTD. 70 patients were treated out whom 35 had mRCC. The MTD was 6.0 mcg/kg/week with one year of treatment well tolerated with dose modifications. The PK data demonstrated that pIFN was readily absorbed and the AUC at weeks 1 and 4 demonstrated a dose-related but not dose-proportional increase over the 0.75 to 7.5 mcg/kg dose range.

The toxicity profile of pIFN is summarized in the below four tables (Figures 1-2 to 1-5) showing AE from three separate trials using pIFN in mRCC patients. Some of the more common and dose-dependent AEs include fatigue, fevers, diarrhea, nausea, myalgias, asthenia and flu-like symptoms.

Figure 1-2: Most Frequently Reported Treatment-Emergent Adverse Events (all grades) by Pegylated IFN α -2b Dose Cohort Over 12 Weeks (core phase)²⁶

Adverse Event	Dose Cohort (µg/kg/wk)											
	0.75 (n = 3)		1.5 (n = 3)		3.0 (n = 4)		4.5 (n = 6)		6.0 (n = 29)		7.5 (n = 25)	
	No. of Patients	%	No. of Patients	%	No. of Patients	%	No. of Patients	%	No. of Patients	%	No. of Patients	%
Nausea	3	100	1	33	2	50	4	67	23	79	20	80
Anorexia	3	100	3	100	2	50	4	67	20	69	19	76
Fatigue	3	100	2	67	4	100	1	17	17	59	21	84
Rigors	1	33	2	67	4	100	2	33	18	62	21	84
Headache	2	67	2	67	3	75	0		17	59	17	68
Vomiting	2	67	2	67	0		3	50	14	48	15	60
Diarrhea	1	33	2	67	0		2	33	12	41	17	68
Injection-site reaction	2	67	3	100	3	75	1	17	16	55	7	28
Myalgia	0		1	33	1	25	2	33	9	31	18	72
Dyspnea	2	67	2	67	0		2	33	12	41	8	32
Fever	1	33	2	67	3	75	2	33	19	66	17	68
Asthenia	2	67	1	33	0		0		9	31	13	52
Pain	1	33	1	33	2	50	1	17	10	34	8	32
Back pain	2	67	1	33	2	50	2	33	9	31	7	28
Dizziness	2	67	0		2	50	0		10	34	8	32
Dry mouth	1	33	2	67	0		1	17	10	34	6	24

Figure 1-3: Most Frequently Reported Treatment-Emergent Adverse Events by Severity (n=29) Over 1 Year (extension phase) using Pegylated IFN α -2b²⁶

Adverse Event	All Grades		Grade 3 or 4	
	No. of Patients	%	No. of Patients	%
Fatigue	11	38	0	
Anorexia	10	34	0	
Pain	10	34	1	3
Headache	9	31	1	3
Injection-site reaction	8	28	0	
Myalgia	8	28	0	
Weight loss	8	28	0	
Nausea	7	24	0	
Alopecia	6	21	0	
Coughing	6	21	0	
Dyspnea	6	21	0	
Fever	6	21	1	3
Rigors	6	21	1	3
Laboratory abnormalities				
Thrombocytopenia	22	76	1	3
Leukopenia	20	69	2	7
Neutropenia	15	52	3	10

Figure 1-4: Toxicity. Grade 1-3, reported at least once during treatment with Pegylated IFN α -2b in mRCC⁴⁸

Toxicity. Grade 1-3, reported at least once during treatment, n = 28 (%)

Side effect	≤ 2 months	> 2 months
Fatigue	23 (82)	28 (100)
Nausea	18 (64)	16 (57)
Fever	16 (57)	11 (39)
Rigors/Chills	10 (36)	8 (29)
Myalgia	9 (32)	8 (29)
Diarrhoea	7 (26)	3 (11)
Other Neurological Events	8 (29)	10 (36)
Artralgia	7 (26)	4 (14)
Mood	6 (21)	4 (14)
Anorexia	6 (21)	7 (26)
Skin-Rash	5 (18)	8 (29)
Headache	5 (18)	6 (21)
Diaphoresis	5 (18)	3 (11)
Vomiting	4 (14)	3 (11)
Alopecia	3 (11)	3 (11)
Weight loss	1 (4)	7 (26)
Cardiac-Dysrhythmia	2 (7)	1 (4)

Figure 1-5: Patient Toxicities with Pegylated IFN α -2b in mRCC (no grade 4 toxicities were observed)²⁵

Toxicity	Grade 2, n (%)	Grade 3, n (%)
Laboratory		
Neutropenia	7 (22)	4 (13)
Lymphopenia	0	4 (13)
Anemia	5 (16)	2 (6)
Thrombocytopenia	2 (6)	1 (3)
Hyperkalemia	8 (25)	3 (9)
Transaminitis	6 (19)	2 (6)
Hyponatremia	0	3 (9)
Symptoms		
Fatigue	8 (25)	4 (13)
Rash	1 (3)	2 (6)
Depression	0	2 (6)
Diarrhea	0	1 (3)

Of note, there are some notable rare toxicities that are known to occur with pIFN. These include:

1. Neuropsychiatric events: Life-threatening or fatal neuropsychiatric events, including suicide, suicidal and homicidal ideation, depression, relapse of drug addiction/overdose, and aggressive behavior have occurred in patients with and without a previous psychiatric disorder during PEG-Intron treatment and follow-up.
2. Bone marrow toxicity: Severe cytopenias may occur. Very rarely alpha interferons may be associated with aplastic anemia.
3. Endocrine disorders: pIFN can cause or aggravates hypothyroidism and hyperthyroidism. Hyperglycemia has been observed in patients treated with PEG-Intron. Diabetes mellitus has been observed in patients treated with alpha interferons.

Patients with these conditions who cannot be effectively treated by medication should not begin PEG-Intron therapy. Patients who develop these conditions during treatment and cannot be controlled with medication should not continue PEG-Intron therapy.

4. Cardiovascular events: Cardiovascular events, which include hypotension, arrhythmia, tachycardia, cardiomyopathy, angina pectoris, and myocardial infarction, have been observed in patients treated with PEG-Intron. PEG-Intron should be used cautiously in patients with cardiovascular disease.
5. Pulmonary disorders: Dyspnea, pulmonary infiltrates, pneumonia, bronchiolitis obliterans, interstitial pneumonitis and sarcoidosis some resulting in respiratory failure and/or patient deaths, may be induced or aggravated by PEG-Intron or alpha interferon therapy. Recurrence of respiratory failure has been observed with interferon rechallenge. PEG-Intron combination treatment should be suspended in patients who develop pulmonary infiltrates or pulmonary function impairment. Patients who resume interferon treatment should be closely monitored.
6. Colitis: Fatal and nonfatal ulcerative or hemorrhagic/ischemic colitis have been observed within 12 weeks of the start of alpha interferon treatment. Abdominal pain, bloody diarrhea, and fever are the typical manifestations. PEG-Intron treatment should be discontinued immediately in patients who develop these symptoms and signs. The colitis usually resolves within 1-3 weeks of discontinuation of alpha interferons.
7. Pancreatitis: Fatal and nonfatal pancreatitis has been observed in patients treated with alpha interferon. PEG-Intron therapy should be suspended in patients with signs and symptoms suggestive of pancreatitis and discontinued in patients diagnosed with pancreatitis.
8. Autoimmune disorders: Development or exacerbation of autoimmune disorders (e.g. thyroiditis, thrombocytopenia, rheumatoid arthritis, interstitial nephritis, systemic lupus erythematosus, psoriasis) have been observed in patients receiving PEG-Intron. PEG-Intron should be used with caution in patients with autoimmune disorders.
9. Ophthalmologic disorders: Decrease or loss of vision, retinal artery or vein thrombosis, retinal hemorrhages and cotton wool spots, optic neuritis, and papilledema are induced or aggravated by treatment with PEG-Intron or other alpha interferons. All patients should receive an eye examination at baseline. Patients with preexisting ophthalmologic disorders (e.g. diabetic or hypertensive retinopathy) should receive periodic ophthalmologic exams during interferon alpha treatment. Any patient who develops ocular symptoms should receive a prompt and complete eye examination. PEG-interferon treatment should be discontinued in patients who develop new or worsening ophthalmologic disorders.
10. Hypersensitivity: Serious, acute hypersensitivity reactions (e.g., urticaria, angioedema, bronchoconstriction, anaphylaxis) have been rarely observed during alpha interferon therapy. If such a reaction develops during treatment with PEG-Intron, discontinue treatment and institute appropriate medical therapy immediately.

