4.1.1 Definition of Dose Limiting Toxicity

Dose-limiting toxicity (DLT) is any drug related toxicity occurring during the first 28 days on study (cycle 1) that meets the parameters defined in Table 4-3.

Table 4-3. Dose Limiting Toxicity

Any grade 3 or 4 treatment related non-hematologic toxicity regardless of duration, except :

 Grade 3 nausea or Grade 3 vomiting \leq 72 hours that recovers to grade 0-2 with maximal antiemetic therapy. Grade 3 diarrhea that resolves to grade 0-2 with loperamide or diphenoxylate/atropine within 48 hours. Grade 3 hypercholesterolemia, hypertriglyceridemia, hyperglycemia or hypophosphatemia that resolves to grade 0-2 with medical management. Transient electrolyte abnormalities lasting \leq 1 week.
Grade 3 or 4 thrombocytopenia.
Grade 4 neutropenia associated with fever or hospitalization for infection.
Grade 4 neutropenia lasting longer than 5 days.
Any toxicity felt to be possibly or probably related to study medication that causes the patient to miss more than 1 dose of either Ixazomib or pIFN in the first 28 days.
Any unacceptable toxicity (UT) as defined for phase II below (Section 4.5)

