5.2 Exclusion Criteria

Patients meeting any of the following exclusion criteria are not to be enrolled in the study:

1. Female patients who are lactating or have a positive serum pregnancy test during the screening period.
2. Failure to have fully recovered (ie, \leq Grade 1 toxicity) from the reversible effects of prior chemotherapy, radiation therapy or targeted therapy
3. Previous use of interferon, ixazomib or bortezomib.
4. Washout periods for prior therapy are as follows
 - Bevacizumab – last dose must be \geq 6 weeks prior to day 1 of study treatment.
 - Targeted therapy – last dose must be \geq 5 half-lives prior to initiation of day 1 of study treatment.
 - Other chemotherapy, immunotherapy, or radiotherapy – Last dose must be \leq 3 weeks prior to day 1 of study treatment
5. Major surgery within 14 days before enrollment.
6. Radiotherapy within 14 days before enrollment. If the involved field is small, 7 days will be considered a sufficient interval between treatment and administration of the Ixazomib.
7. Untreated central nervous system involvement.
8. Uncontrolled thyroid disease.
9. Infection requiring systemic antibiotic therapy or other serious infection within 14 days before study enrollment.

10. Evidence of current uncontrolled cardiovascular conditions, including uncontrolled hypertension, uncontrolled cardiac arrhythmias, symptomatic congestive heart failure, unstable angina, or myocardial infarction within the past 6 months.
11. Systemic treatment, within 14 days before the first dose of Ixazomib, with strong inhibitors of CYP1A2 (fluvoxamine, enoxacin, ciprofloxacin), strong inhibitors of CYP3A (clarithromycin, telithromycin, itraconazole, voriconazole, ketoconazole, nefazodone, posaconazole) or strong CYP3A inducers (rifampin, rifapentine, rifabutin, carbamazepine, phenytoin, phenobarbital), or use of Ginkgo biloba or St. John's wort.
12. Known ongoing or active systemic infection, active hepatitis B or C virus infection, or known human immunodeficiency virus (HIV) positive.
13. Decompensated liver disease (Child-Pugh score >6) or active or past auto-immune hepatitis.

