14. Any serious medical or psychiatric illness that could, in the investigator's opinion, potentially interfere with the completion of treatment according to this protocol. In particular, a history of a serious psychiatric illness that might be exacerbated by IFN- α -2b; a history of significant or unstable cardiovascular, hepatic or gastrointestinal disease; a history of autoimmune disease of any kind.
15. Known allergy to any of the study medications, their analogues, or excipients in the various formulations of any agent.
16. Known GI disease or GI procedure that could interfere with the oral absorption or tolerance of ixazomib including difficulty swallowing.
17. Evidence of another clinically or radiographically active invasive malignancy OR Diagnosed or treated for another malignancy within 2 years before study enrollment or previously diagnosed with another malignancy and have any evidence of residual disease. Patients with nonmelanoma skin cancer or carcinoma in situ of any type are not excluded if they have undergone complete resection.
18. Patient has \geq Grade 3 peripheral neuropathy, or Grade 2 peripheral neuropathy with pain on clinical examination during the screening period.
19. Having received an investigational agent with 21 days of receiving the first dose of study drug on this trial.

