5.3 Participant Registration

5.3.1 Patient Registration

Eligible patients will be entered on study centrally by the Fox Chase Cancer Center QA Coordinator or their designee. Following registration, patients should begin protocol

treatment within 7 days of registration. If a patient does not receive protocol therapy following registration, the patient's registration on the study may be cancelled and the subject will be replaced. The QA Coordinator should be notified of cancellations as soon as possible.

Subjects may be registered from 9:00 am to 5:00 pm excluding holidays by calling the QA Coordinator at [contact]. The site's investigator or designee will then fax the completed registration form, consent and HIPAA signature pages and eligibility checklist to [contact]. The QA Coordinator or designee will notify the site by phone and fax when registration is confirmed and the sequence number has been assigned. Subjects must be registered and have received a sequence number assigned by the QA Coordinator prior to the initiation of treatment. The following forms must be completed at the time of registration:

- Signed and dated informed consent form
- Signed and dated HIPAA consent form
- Registration form
- Signed eligibility checklist

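### The protocol's rule against starting pegylated interferon in medication-refractory endocrine disease is a named exclusion for thyroid disease but not for diabetes or hyperglycemia

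*Combined protocol and SAP*

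**What the plan says.** Section 1 ends with ten numbered toxicities of pegylated interferon, introduced as notable but rare. Item 3, on endocrine disorders, says the drug can cause or aggravate hypothyroidism and hyperthyroidism. It adds that hyperglycemia has been seen with this product and diabetes mellitus with alpha interferons. Two instructions follow. The first concerns starting: "Patients with these conditions who cannot be effectively treated by medication should not begin PEG-Intron therapy". The second concerns continuing: "Patients who develop these conditions during treatment and cannot be controlled with medication should not continue PEG-Intron therapy".

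Section 5.2 opens with a binding sentence: "Patients meeting any of the following exclusion criteria are not to be enrolled in the study". Item 8 of that list reads, in full, "Uncontrolled thyroid disease". Item 14 is a general clause for serious medical or psychiatric illness that, in the investigator's opinion, could "potentially interfere with the completion of treatment according to this protocol". It goes on to single out certain histories, including "a history of autoimmune disease of any kind". Item 2 excludes patients who have not recovered to Grade 1 or better from the reversible effects of earlier chemotherapy, radiotherapy or targeted therapy.

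The Schedule of Events collects HbA1c at screening, with a footnote (10) giving worsening of diabetes by the interferon as the reason. Glucose is part of the screening serum chemistry (footnote 6). An eye evaluation is scheduled for patients with a history of diabetic or hypertensive retinopathy (footnote 11).

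**The concern.** The rule on starting treatment follows all four conditions and nothing limits it to thyroid disease. The eligibility list carries over one half by name and leaves out the other. The situation can plausibly arise at entry: the schedule measures HbA1c because of this drug effect and anticipates patients with diabetic retinopathy. Yet no eligibility item says what follows from a finding of uncontrolled diabetes.

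What is at stake is patient safety at enrolment. If the investigator does not apply exclusion 14, a patient whose diabetes or hyperglycemia cannot be controlled with medication could meet every listed criterion. That patient would then receive a drug that the protocol says can make the condition worse, against the protocol's own advice not to start.

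**Working it through.** No figure in the plan bears on this point, so the check compares texts.

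**Step 1. Scope of the rule.** Item 3 of the Section 1 list names hypothyroidism, hyperthyroidism, hyperglycemia and diabetes mellitus before giving the instruction on starting. The phrase referring back to these conditions therefore covers a thyroid half and a glucose half.

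**Step 2. Search of the eligibility list.** Section 5.1 has 10 items and Section 5.2 has 19, so 10 + 19 = 29.

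| Half of the rule | Items naming it | Where |
|---|---|---|
| Thyroid disease | 1 of 29 | Exclusion 8 |
| Diabetes, hyperglycemia, glucose or HbA1c | 0 of 29 | none |

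The laboratory limits in inclusion 7 cover neutrophils, platelets, hemoglobin, bilirubin, ALT/AST and creatinine clearance. They include no glucose measure.

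**Step 3. Indirect routes to exclusion.**

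- Exclusion 14, general clause. Diabetes that medication cannot control may be a serious illness that threatens completion of treatment, particularly because the second instruction in item 3 would call for stopping interferon. The clause turns on the investigator's opinion about completing treatment. The Section 1 rule asks something else: whether medication can effectively treat the condition. The examples in exclusion 14 are psychiatric, cardiovascular, hepatic, gastrointestinal and autoimmune disease, with no endocrine entry.
- Exclusion 14, autoimmune history. This can reach diabetes of autoimmune origin, but not other diabetes.
- Exclusion 2. This can reach hyperglycemia above Grade 1 that is a reversible effect of earlier treatment, but not long-standing disease.

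None of these makes refractory diabetes or hyperglycemia an exclusion as such.

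**Step 4. Rules that act after dosing.**

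| Rule | What it addresses |
|---|---|
| Section 1, item 3, instruction on continuing | Conditions that develop during treatment |
| Section 4.1.1 and Table 4-3 | "any drug related toxicity occurring during the first 28 days on study" meeting the listed parameters, with an exception for Grade 3 hyperglycemia that resolves with medical management |
| Section 4.5 | Related, clinically significant Grade 4 non-hematologic toxicity leads to withdrawal |
| Section 6.3 | A new cycle may start once toxicity returns to Grade 1 or less, or to the patient's baseline |
| Table 6-3 | Interferon is held for related Grade 3 non-hematologic toxicity; discontinuation is considered for Grade 4 |
| Section 7.1.1 | A prior condition that worsens counts as an adverse event |

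Each rule responds to something new or worse after exposure. Section 6.3 also takes the patient's baseline as an acceptable endpoint, so poor control already present at entry would not hold up a cycle. None of them answers whether the patient should have started.

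**Step 5. Comparison with the other interferon hazards.** Of the ten items in the Section 1 list, item 3 is the only one with an instruction not to begin. Cardiovascular disease (item 4) and autoimmune disorders (item 8) carry only advice to use caution, yet both appear by name in Section 5.2 (exclusions 10 and 14 for cardiovascular disease, 14 for autoimmune disease). The glucose half of the strongest entry instruction is thus handled less explicitly than two hazards with weaker wording.

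**The case against.** The best case for the plan is that the rule is already in the protocol. Section 10.2 requires the study to be run as the protocol describes, so starting interferon in such a patient would contradict Section 1 whatever Section 5.2 lists. Exclusion 14 fits the case, and once the investigator makes that judgment the Section 5.2 lead-in makes exclusion mandatory. The investigator has HbA1c and glucose to hand. The proposed wording sets no threshold, so the same person would judge the same data. Worsening after entry is covered by several rules.

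Much of this stands. A reader might infer that the protocol has no means of keeping these patients out. The documents do not support that: exclusion 14, and exclusion 2 in narrow cases, can be used. Nor do they support the inference that an enrolled patient would be unprotected, since Section 4.5, Table 6-3 and Section 7.1.1 address deterioration.

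A reader might also infer that the eligibility check at registration lacks a glucose prompt. Section 5.3.1 requires a "Signed eligibility checklist", but its content is not in the documents, so nothing can be said about what it contains.

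What the objection does not remove is the difference between a named criterion and one that depends on opinion. Exclusion 14 need not be invoked, and it asks about completing treatment rather than whether medication can control the condition. The general clause could equally have covered uncontrolled thyroid disease, which the plan nevertheless lists separately.

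**Conclusion.** The point holds as a minor safety-consistency gap. Section 1 advises against starting interferon for thyroid and glucose disorders that medication cannot effectively treat, but only the thyroid half is a named exclusion. The glucose half is reachable only indirectly, and rules that act after exposure are not a substitute.

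This rests on reading the Section 1 instruction as covering all four conditions listed before it, which is its plain sense, and on the current text of Sections 5.1 and 5.2. The number of patients affected cannot be estimated: the documents give no prevalence of refractory diabetes or hyperglycemia in this population, and none is assumed here. It would go too far to infer that dose-finding or the phase II conclusions are distorted. No sample size, power or error rate depends on this criterion, and nothing in the documents shows that such patients would be enrolled in any number.

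**What to change.** Extend exclusion 8 so that it reads: *Uncontrolled thyroid disease, or diabetes mellitus or hyperglycemia not controlled with medication*. The investigator would judge this from the HbA1c and serum glucose already collected at screening. A raised HbA1c alone need not exclude a patient whose disease can be treated. Judgment remains, but it is directed at the protocol's own question, and exclusion becomes mandatory once the answer is that medication does not control the condition.

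The cost is one added phrase in Section 5.2 and no new test. A few candidates may be excluded, but these are patients whom Section 1 already advises should not start.

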6.3 Dose-Modification Guidelines

Treatment with Ixazomib and Pegylated IFN- α -2b will use a cycle length of 28 days. Evaluations will occur as listed in the Study Calendar. For a new treatment cycle to begin, the patient must meet the following criteria:

- ANC must be $\geq 1,000/\text{mm}^3$.
- Platelet count must be $\geq 75,000/\text{mm}^3$.
- Hemoglobin must be $\geq 8.0 \text{ g/dL}$.
- All other non-hematologic toxicity (except for alopecia) must have resolved to \leq Grade 1 or to the patient's baseline condition

If the patient fails to meet the above-cited criteria for initiation of the next treatment, dosing should be delayed for 1 week for both drugs. If the patient continues to fail to meet the above-cited criteria, delay therapy and continue to re-evaluate. The maximum delay before treatment should be discontinued will be 4 weeks or at the discretion of the Principal Investigator.

For dosing recommendations upon recovery, refer to Table 6-1, Table 6-2 and Table 6-3. If starting doses will be different than below, the protocol will be amended prior to moving on to Phase II.

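### Three of the five grade 4 rows in Table 6-3 let treatment go on where Section 4.5 requires withdrawal; secondarily, four pIFN stops in Section 1 never reach the dosing rules

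*Combined protocol and SAP*

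**What the plan says.** **Grade 4.** Section 4.5 defines UT and says that a patient who develops it at any point leaves the study. The definition covers a grade 4 non-hematologic event that is clinically significant and judged definitely, probably or possibly related. Table 6-3 has five grade 4 rows: peripheral neuropathy, rash, diarrhea, nausea/vomiting, and a catch-all for other related non-hematologic events. They do not all lead to withdrawal.

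**pIFN stops.** Section 1 lists ten notable rare pIFN toxicities. Four of them concern us here:

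- Colitis (item 6): "PEG-Intron treatment should be discontinued immediately in patients who develop these symptoms and signs".
- Pancreatitis (item 7): suspend on suspicion, and "discontinued in patients diagnosed with pancreatitis".
- Eye (item 9): "PEG-interferon treatment should be discontinued in patients who develop new or worsening ophthalmologic disorders".
- Serious acute hypersensitivity (item 10): "If such a reaction develops during treatment with PEG-Intron, discontinue treatment and institute appropriate medical therapy immediately".

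Section 6.3 points staff elsewhere: "For dosing recommendations upon recovery, refer to Table 6-1, Table 6-2 and Table 6-3". Neither Table 6-3 nor the termination list in 6.13 names any of the four. Section 6.13 does list unacceptable adverse events and investigator judgment as grounds to end treatment, and it ends treatment permanently once a toxicity delay reaches 21 days.

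**The concern.** A physician facing a related grade 4 diarrhea or vomiting event has two opposite written instructions: withdraw the patient, or reduce and resume. The protocol does not say which prevails. UT is also the toxicity endpoint behind the stopping and decision rules in Section 8.1.2, so what follows a UT should be the same for every patient.

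The second issue is one of reach. The pIFN stops sit in the background section, while the dosing rules that staff are told to use say hold and resume. Section 1 describes colitis and pancreatitis on interferon as sometimes fatal. Whether pIFN is stopped then depends on someone recalling the background text.

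**Working it through.** No sample-size or power figure is involved, so the check sets the texts side by side.

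**Step 1. Grade 4 rows of Table 6-3 against Section 4.5**

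| Grade 4 row | Action in Table 6-3 | Against 4.5 |
|---|---|---|
| Rash | Stop study treatment, both drugs | Agrees |
| Peripheral neuropathy | Stop study drug | Broadly agrees; 6.2 also uses that term for the ixazomib capsules |
| Diarrhea | Hold both; resume ixazomib two levels lower and pIFN one level lower; withdraw only if no such level is left | Conflicts if the event is UT |
| Nausea/vomiting | Same as diarrhea | Conflicts if the event is UT |
| Other related events | Stopping is to be considered; exception for clinical benefit | Conflicts less sharply |

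Count: 3 of 5 rows conflict.

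Doses under the Table 6-1 example (4.5 mcg/kg/week and 4.0 mg) after grade 4 diarrhea or vomiting:

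- pIFN, one level down: 4.5 to 3.0 mcg/kg/week, (4.5 − 3.0)/4.5 = 33% lower.
- Ixazomib, two levels down: 4.0 to 2.3 mg, (4.0 − 2.3)/4.0 = 42.5% lower.
- Under 4.5: neither drug, because the patient is withdrawn.

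In the first 28 days the table stands against two sections, not one. A UT is a DLT under 4.1.1, and 4.2 ends treatment on DLT.

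**Step 2. The four Section 1 stops against the dosing rules**

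Named in Table 6-3: 0 of 4. Named in 6.13: 0 of 4. The 6.4 diarrhea text mentions blood in the stool and fever, but only to advise against two antidiarrheals; it does not mention stopping pIFN. After cycle 1, a related grade 3 event is handled as follows:

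- Diarrhea or nausea/vomiting row: hold both drugs, then resume both one level lower. In the example pIFN restarts at 3.0 mcg/kg/week.
- Generic rows (both drugs, or IFN only): hold until recovery. No restart dose is given for recovery within 4 weeks; a reduction is specified only when recovery takes longer.

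**Step 3. Do other rules close the gap?**

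- *DLT.* In cycle 1 a related grade 3 event is in general a DLT. Section 1 places colitis within 12 weeks of starting interferon, which is 84 days. The part after cycle 1 is 84 − 28 = 56 days, or 56/84 = 67% of that window. This is a share of time, not of cases.
- *The 21-day stop in 6.13.* On colitis, Section 1 adds: "The colitis usually resolves within 1-3 weeks of discontinuation of alpha interferons". That is 7 to 21 days, so even if a pIFN hold counts as a treatment delay, the rule is reached only at the upper end.
- *Discretion in 6.13.* It permits a stop and does not require one for these conditions.

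**The case against.** **On grade 4.** The diarrhea and vomiting rows state no attribution, so they could be meant for unrelated events. The catch-all row could serve related events that are not clinically significant, which 4.5 leaves out. Both readings are possible, but the table states neither, and the clinical-benefit exception has no such limit. A reader might infer that every grade 4 row conflicts with 4.5. That is not so: rash agrees and neuropathy broadly agrees.

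**On Section 1.** The stops are in the protocol in directive language, and a specific instruction would normally govern a generic row. That stands: the defect is one of placement and precedence, not a missing stop. It does not remove the problem, because 6.3 sends staff to the tables and no text ranks Section 1 above them.

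Stronger readings that the documents do not support:

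- *Section 1 forbids any restart.* It never says the stop is permanent. The bar is inferred from its contrast between suspending and discontinuing, and from item 5, where a restart is foreseen: "Patients who resume interferon treatment should be closely monitored".
- *Every restart under the generic rows is at full dose.* This would follow if the 21-day stop always pre-empted the 4-week reduction step (28 − 21 = 7 days later). But the delay limits differ: 4 weeks or PI discretion in 6.3, 3 weeks or PI discretion in Table 6-2, and 21 days in 6.13. A reduced restart after 4 weeks is therefore possible.
- *The table tells staff to treat on through grade 2 colitis.* Only if colitis is handled as plain diarrhea.
- *Low-grade eye disorders conflict.* Below grade 3 no row applies, so Section 1 is the only instruction.
- *The endocrine item is a fifth restart gap.* A disorder that medication cannot control would hardly meet the recovery condition, so I leave it out.

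**Conclusion.** The main point holds: three of five grade 4 rows in Table 6-3 allow continuation where 4.5 requires withdrawal. It is clear for diarrhea and nausea/vomiting when the event is related and clinically significant, and weaker for the catch-all row. I read study drug in the UT definition as either agent.

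The secondary point also holds: four Section 1 pIFN stops appear in neither Table 6-3 nor 6.13, and after cycle 1 the grade 3 rows let pIFN resume. It amounts to a contradiction only if discontinuing is taken to exclude restarting, which is the natural reading but an inference.

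Section 1 calls these pIFN toxicities rare and the documents give no rates, so I claim no number of patients affected and no change in the design's operating characteristics. The case for correction is that the instructions conflict on potentially serious events and the remedy is cheap.

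**What to change.** **Grade 4 rows.** In the diarrhea, nausea/vomiting and catch-all rows, state that an event meeting the 4.5 definition of UT leads to withdrawal. Limit reduce-and-resume to grade 4 events that are not UT, and remove the clinical-benefit exception for UT.

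**Section 1 stops.** State in 6.3, in Table 6-3 and in 6.13 that the stops for colitis, diagnosed pancreatitis, eye disorders and serious acute hypersensitivity take precedence over the table rows. Then:

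- Say that pIFN is not restarted after colitis, diagnosed pancreatitis or serious acute hypersensitivity.
- Define the colitis trigger as a combination, namely bloody diarrhea with abdominal pain or fever, and repeat it in the 6.4 diarrhea text. A single symptom would stop too many: at 4.5 mcg/kg/week, Figure 1-2 shows diarrhea in 2 of 6 patients (33%) and fever in 2 of 6 (33%).
- Limit the eye stop to a disorder confirmed on the prompt examination that item 9 already calls for. A stop for any eye complaint of any grade would be too broad.

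**Cost.** Text edits and notice to the team at a single center; no new visit or procedure. The downside is that a few patients who might have resumed treatment will stop.
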